Clinical Study Protocol

ClinicalTrials.gov entry no.	NCT05029739
Version number	1.0
Date of ethical approval	July 13, 2021

A Mobile Intervention for Patients with Peripheral Artery Disease (I-PAD): a Prospective Randomized Open Blinded End-point (PROBE) study

I. BACKGROUND AND SIGNIFICANCE

Peripheral artery disease (PAD) is a highly prevalent atherosclerotic syndrome with an estimated global population burden of ~200 million people (1). Patients with PAD are at heightened risk for adverse cardiovascular and limb events and impaired quality of life (2). Cigarette smoking is the most important modifiable risk factor for PAD. Patients with PAD who smoke have higher disease progression rates, greater risk of complications, poor post-procedural outcomes, compromised functional status, and increased hospitalizations, accounting for a higher patient and societal burden (3).

A significant goal of PAD treatment includes risk factor modification and prevention of cardiovascular events. Guideline directed therapy includes cardioprotective pharmacotherapies (i.e., antiplatelet therapy; statins; and blood pressure control, preferably with angiotensin-converting enzyme inhibitors (ACE-I) or angiotensin receptor blockers (ARBs)), and lifestyle modification (i.e., changes in diet, physical activity, and smoking cessation) (2). Nevertheless, adherence to pharmacologic and lifestyle recommendations in PAD is uncertain (4). Effective non-pharmacologic therapies for PAD also exist, including smoking cessation, exercise support, and diet counseling (5). However, limited data is available on mobile applications offering digitally delivered lifestyle change support, including a structured exercise program and smoking cessation support (6). This study aims to digitally provide lifestyle change support, including a structured and PAD-focused lifestyle program and smoking cessation support via a mobile platform (Sidekick Health) with the primary aim to increase patients' walking ability and secondary aims to reduce smoking and improve medication adherence.

II. SPECIFIC AIM

The specific aim is to determine whether a 12-week digitally delivered behavior change intervention for patients with peripheral artery disease increases walking ability, reduces smoking, improves quality of life and improves medication adherence. A follow-up visit after 12 months will be planned, to assess longer term effect on outcomes and healthcare cost.

Hypotheses

- a) At the end of the 12 weeks, the interventional arm will reach a clinically meaningful change in walking ability, as compared to controls, measured by a change in the 6-MWT at twelve-week, and 12 months; the minimal clinically important difference (MCID) is defined as +12m (7).

- b) At the end of the 12 weeks, $\geq 15\%$ interventional treatment arm participants will give up smoking or have significantly reduced their daily smoking compared to less than $\leq 10\%$ in the control arm.
- c) At the end of the 12 weeks, $\geq 50\%$ of interventional treatment arm participants will improve their medication adherence from pre- until post-intervention as compared to $< 30\%$ in the control arm.
- d) Healthcare cost will be reduced at 12 month follow-up in the intervention arm.

III. METHODOLOGY

We will implement a randomized controlled study of a 12-week lifestyle intervention for patients with peripheral arterial disease, delivered via the digital platform Sidekick Health. Participants will be recruited and randomized in a 1:1 manner to the digitally delivered intervention + standard of care or standard of care only. The standard of care group will receive an information leaflet on important lifestyle factors for PAD and smoking cessation and medical adherence will be encouraged by the health care provider. The interventional arm will receive a digital program delivered to their mobile phone alongside standard of care. Replicating a real-life scenario a personalized approach will be applied in the interventional arm, especially regarding smokers. Therefore, two pathways are possible in the interventional arm in this trial, one for smokers who want assistance in smoking cessation (PAD-SC) and another for non-smokers or those who smoke and do not desire to quit (PAD-Reg). Patients will be followed up at 12 weeks. We aim to do a separate follow-up at twelve months. The primary outcome will be a change in pain-free and maximal walking ability, measured by the 6-minute walking test. Secondary outcomes will include smoking status change (in PAD-SC group as compared to the control arm), medication adherence and lifestyle changes (increased physical activity, changes in self-assessed stress/energy/sleep quality levels), health-related quality of life, and a reduced need for hospitalization or revascularization due to PAD at 12 months of follow up.

Subject selection

Individuals willing to participate and who provide written informed consent to the study will be further assessed and screened based on the inclusion and exclusion criteria presented in Table 1.

Table 1. Participant Criteria

Inclusion	Exclusion
Adults with confirmed PAD referred to a vascular surgery unit for evaluation and treatment, currently on best medical treatment and own/have access to a mobile smartphone	Critical limb ischemia, prior amputation, or other diseases/impairment that limit the walking ability and the 6-minute walk test's proper conduct
Stable PAD disease and limb symptoms during the last 3 months.	Cognitive impairment
PAD is the activity-limiting disease	Prior revascularization less than one year ago
Abnormal resting ankle-brachial index (≤ 0.90), falsely elevated above 1.3 or a 30% post-exercise ABI reduction.	A planned revascularization procedure during the upcoming 12 months (known at baseline)

Subject enrollment

Patients will be recruited by a clinic nurse or a medical doctor at participating centers (via telephone or during a scheduled in-person visit). Once agreed to participate and after signing informed consent, then the inclusion and exclusion criteria will be explored. Patients failing the screening process (do not meet the inclusion/exclusion criteria) may not participate in this study. Reasons for screen failure will be documented, but no other data will be collected. Participants who meet the criteria will be randomized to intervention or usual care in a 1:1 manner.

Based on a G*power analysis, the total number of patients in the two groups (intervention and control) will be 134, 67 in the intervention group and 67 in the control group, with an anticipated effect size of $f = 0.15$, $\alpha = 0.05$, power = 0.80 and correlations between time points (baseline and final timepoint) estimated at $r=0.25$. Foreseeing an attrition rate of 15%, we aim to recruit 155 patients to the trial.

Study procedures

All participants:

After recruitment, measurements and data collections will occur at each clinic by a experienced clinic or research nurse, as shown in table 2 and further detailed under section VIII. Furthermore, a 6-minute walking test will be administered by a trained clinic nurse at baseline, after 12 weeks and for a separate follow-up at 12 months. The American Thoracic Society protocol for the 6-minute walking test, modified for patients with intermittent claudication (IC), will be used. The 6MWT has excellent test-retest reliability for patients with IC. (8, 9). A central computerized procedure will randomly assign participants to treatment arms, stratified for study site and smoking status.

Intervention:

Participants will be instructed to download the SKH mobile app, and they will receive an access code to activate the PAD lifestyle change program. After the first week of the program, participants who smoke will be offered to incorporate smoking cessation support into their PAD program. These changes are minor and not intended to divide the intervention group in two but instead personalize the experience. Personalization of the program is essential for engagement and to deliver the most meaningful impact on clinical outcomes. The program aims to empower positive lifestyle change by gamification, altruistic rewards, and engaging content with relevant tasks or missions to be completed. Beyond this, all patients in the interventional arm will also receive standard of care as defined below for the control arm.

Participants in the intervention group will also be asked to do a separate and virtually delivered 6-minute walking test to validate the digital in-app 6MWT.

Control:

All patients in the control arm will receive best medical treatment including start or optimization of secondary preventive pharmacotherapy, smoking cessation advise and advise on modifiable risk factors. The control arm will also receive an information leaflet about relevant lifestyle modifications for PAD. After baseline measurements and data collection, there will be no scheduled visits by a health care provider until week 12.

Table 2. Timing of Proposed Data Collection and Instruments Used

Data collection/Instruments	Baseline	Post-Intervention (after week 12)	12-month follow-up
All participants (intervention and control)			
Demographic and Clinical/Medical Baseline Information (e.g., tobacco use, other risk factors, and comorbidities)	Yes	Yes	Yes
6-Minute Walking Test	Yes	Yes	Yes
Vascular Quality of Life Questionnaire (VascuQoL-6)	Yes	Yes	Yes
Morisky Medication Adherence Scale (MMAS-8)	Yes	Yes	Yes
Quality of life questionnaire – assessed by EQ5D5L	Yes	Yes	Yes
Assessment of health literacy (HLS-EU-Q16 Swedish version)	Yes	-	-
Carbon Monoxide breath monitor (smokers only)	Yes	Yes	Yes
Smoking Readiness to Quit Ladder (smokers only)	Yes	Yes	Yes
Daily frequency of cigarettes smoked (smokers only)	Yes	Yes	Yes
Intervention arm only			
In-app 6-minute walking test	Yes	Yes	Yes
Free-living physical activity (measured as total step count per day)	Yes (week 1)	Yes	-
In-app metrics (e.g. stress/sleep/energy level self-assessment)	Yes (week 1)	Yes	-

Measures – copies of questionnaires will be included in this protocol when finalized in section VIII below (Study Questionnaires)

IV. BIOSTATISTICAL ANALYSIS

Variables to be collected

Participants' demographic and background information, including age, gender, height, weight (and BMI), tobacco use, co-morbid medical or psychiatric conditions, and information on any current medical therapy they may or may not be receiving will be collected. All participants should be on the best medical PAD treatment available for them, and the control arm will receive an information leaflet about relevant lifestyle modifications for PAD. A 6MWT, questionnaires, and validated survey instruments (10) will be administered both pre-and post-intervention and 12 months from the start of the intervention.

Primary Outcomes (Intervention KPIs)

As far as possible, evaluation of endpoints will be done by evaluators blinded to the treatment assignment (PROBE design).

- Walking Ability: Change in patients objectively measured walking ability (measured by the 6-Minute Walk Distance Test) from pre- to post-intervention and 12 months.

Secondary Outcomes

- Smoking status: Change in patients' daily smoking patterns from pre to post-intervention and at twelve months. This will be based on information from the patient, supported by read-outs from the carbon monoxide breath monitor at baseline, 12 weeks and one year.
- Medication adherence improvement.
- Lifestyle behavioral changes (measured in-app):
 - Changes in free living physical activity, measured as total step count per day (from baseline to week 12)
 - Changes in self assessed stress levels, measured on an ordinal scale from 0-10 (from baseline to week 12)
 - Changes in self assessed energy levels, measured on an ordinal scale from 0-10 (from baseline to week 12)
 - Changes in self assessed sleep quality, measured on an ordinal scale from 0-10 (from baseline to week 12)

- Disease-specific health-related quality of life.
- Increased readiness to quit smoking.
- Comparing outcomes to health literacy.
- Comparing healthcare costs between groups. Following completion of the long-term follow-up at 12 months for all patients, a separate cost-effectiveness analysis will be undertaken, based on the prospectively collected EQ5D-5L data and accumulated costs per patient as registered in the participating hospital's cost-per-patient databases. Quality Adjusted Life Years (QALYs) and Incremental Cost-Effectiveness Ratio (ICER) will be the main analyzed endpoints.

[figure not shown]
Retention and Engagement

- Program uptake (number of app downloads, how many participants/potential quitters registered (including gender and age)
- Length of program participation
- Program usage patterns (how often do people visit, how many tasks are performed, which tasks (videos, daily tasks, other) are used/accessed, etc.)
- Pre/post assessment of medication therapy (as registered medication taken)

End of study

The formal trial completion is when the recruited patients have completed the 12-week intervention, but an extended follow-up at twelve months from study start will also be arranged.

IPAD STUDY DESIGN

Statistical Methods

Analyses will be performed according to the intention-to-treat principle and per-protocol analyses. Baseline characteristics and raw score questionnaire outcomes will be summarized as mean and SD for continuous measures and absolute numbers and percentages in each group. Changes in each outcome between baseline, post-intervention, and later a 12-month follow-up will be compared between and within the groups using t-tests or non-parametric statistical tests as appropriate. For the between-group differences, 95% Confidence Intervals will be reported. Correlations will be run to explore relationships between variables. For the primary outcome analyses, Ancovas or Mixed Anovas (repeated measures anovas) will be used, correcting for covariates that are significantly different between groups. The size of the change in HRQoL will be related to minimal important change values for the VascuQoL-6. It will be further assessed through effect size calculations (effect size=the difference in mean values between baseline and follow-up, divided by the SD at baseline). Cohen's criteria for interpreting effect sizes will be applied (small, 0.2–0.5; moderate, 0.5–0.8 and large, over 0.8). The a priori level for statistical significance will be set at a 2-sided $P < .05$.

V. RISKS AND DISCOMFORTS

We expect minimal to no risks and discomforts to be associated with this study. The lifestyle/behavioral change program is guideline-compliant for PAD patients and has

been reviewed by several medical doctors, behavioral scientists, and specialists in vascular surgery. Psychosocial risks will be minimal as well.

VI. POTENTIAL BENEFITS

Potential Benefits to Participating Individuals

The hope is that the intervention will increase participants' walking ability, reducing IC symptoms and prevent revascularization, empower participants to change their lifestyle and smoking patterns for the better, or that they will quit smoking altogether. Further, this intervention may also improve other patient-reported outcomes (e.g., reduce stress, improve sleep) without causing significant harm. Although the expected benefits are limited for patients that are allocated to usual care in the study, the enhanced follow-up at 12 weeks and 12 months may allow for a more careful evaluation and subsequent treatment of their condition following the end of study.

Potential Benefits to Society

The hope is that this program will contribute to a healthier population. If the Sidekick PAD program proves efficient because it is highly scalable, it may alter the disease progression and improve millions' lives. The program may also positively impact the environment if participants quit smoking as cigarettes are a considerable environmental pollutant.

VII. MONITORING AND QUALITY ASSURANCE

SKH will regularly monitor study data accuracy and will guarantee safe study data storage. Furthermore, SKH will monitor and amend potential technical issues that hinder participants' accurate access to and using the smartphone application and its full functionality. As soon as the opportunity arises, the obtained data will be anonymized and removed from personal health information. All participants will be de-identified and assigned research subject IDs (e.g., participant 1). Only the study staff will have access to information that can link the subject IDs with the personal health information, saved on a secure, shared drive. Further, clinic staff/providers will report any adverse events using standard procedures.

VIII. VARIABLES TO BE COLLECTED

Demographic/clinical/anthropometric variables:

1. Age
2. Gender
3. Smoking status
4. Height
5. Weight

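### Hypothesis (b) sets its 15% and 10% smoking limits on whole arms that include non-smokers, and it conflicts with the PAD-SC versus control definition; the denominator should be baseline smokers in both arms

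*Combined protocol and SAP*

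**What the plan says.** Section II, Hypotheses (b), gives a 12-week responder rate: at least 15% of "interventional treatment arm participants will give up smoking or have significantly reduced their daily smoking compared to less than" 10% "in the control arm". Neither percentage is limited to people who smoke.

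Non-smokers are in both arms. Table 1 has no smoking criterion; its first inclusion entry begins "Adults with confirmed PAD referred to a vascular surgery unit for evaluation and treatment". Section III describes one app pathway for smokers who want help to stop (PAD-SC) and "another for non-smokers or those who smoke and do not desire to quit (PAD-Reg". Randomisation is "stratified for study site and smoking status". Table 2 lists "Daily frequency of cigarettes smoked (smokers only" and restricts the carbon monoxide and readiness measures in the same way.

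The opening of Section III also gives a different comparison for the smoking outcome: "smoking status change (in PAD-SC group as compared to the control arm". Under Study procedures, the offer of cessation support comes after the first week of the program, and the personalisation is said not to be meant to split the intervention group.

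The smoking item under Secondary Outcomes (Section IV) names no denominator. Statistical Methods names no analysis set for smoking beyond general intention-to-treat and per-protocol analyses.

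**The concern.** A non-smoker counted in the denominator of (b) is a non-responder by construction. Each arm's rate is then the smokers' rate multiplied by the smoker share, so 15% and 10% no longer describe success among people who could succeed. Two trials with the same effect in smokers could report quite different percentages because their sites recruited different mixes.

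The PAD-SC definition does not repair this. It removes non-smokers and unwilling smokers from the intervention side only. It also selects on a choice made after randomisation, for which controls have no counterpart.

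With two stated comparisons and no analysis set, the denominator could also be chosen after the results are known.

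**Working it through.** **Inputs from the protocol.** 67 per arm (Subject enrollment); limits of at least 15% and at most 10% (hypothesis b). The smoker share s and the response rates among smokers are not given; every value used for them below is an assumption.

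**The plan's own figure.** The total of 134 reproduces as a repeated-measures ANOVA, group-by-time interaction, two groups and two times. The noncentrality is f² × N × m/(1 − r) = 0.0225 × 134 × 2/0.75 = 8.04, and power is 0.804. The calculation concerns the walking outcome; the protocol gives no sample size or power for (b). Only the 67 per arm is carried forward.

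**Limits in whole persons.** 0.15 × 67 = 10.05, so at least 11 successes. 0.10 × 67 = 6.7, so at most 6.

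**Limits among smokers.** Arm rate = smokers' rate × s. The rate needed is therefore 0.15/s and the control ceiling 0.10/s. The last two columns use whole persons.

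| s (assumed) | Smokers of 67 | 0.15/s | 0.10/s | 11/smokers | 6/smokers |
|---|---|---|---|---|---|
| 20% | 13 | 75% | 50% | 85% | 46% |
| 30% | 20 | 50% | 33% | 55% | 30% |
| 40% | 27 | 37.5% | 25% | 41% | 22% |
| 50% | 34 | 30% | 20% | 32% | 18% |

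**Chance of meeting each limit on the whole-arm reading.** These are binomial, with the number of smokers from the table: P(X ≥ 11) for intervention and P(X ≤ 6) for control.

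| Smokers' rates, intervention v control (assumed) | s = 30% | s = 40% | s = 50% |
|---|---|---|---|
| 15% v 10% | <0.001; 0.998 | 0.001; 0.985 | 0.009; 0.952 |
| 40% v 20% | 0.13; 0.91 | 0.54; 0.71 | 0.86; 0.47 |
| 50% v 30% | 0.41; 0.61 | 0.88; 0.26 | 0.99; 0.08 |

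**The three possible denominators side by side, at s = 30%.** Expected rates, read literally. To isolate the denominator, PAD-SC members are assumed to respond like all intervention smokers, that is, with no self-selection.

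| True rates in smokers | Whole arms | PAD-SC v whole control arm | Baseline smokers, both arms |
|---|---|---|---|
| 20% v 20% (no effect) | 0.20 × 0.30 = 6% v 6% | 20% v 6% | 20% v 20% |
| 40% v 20% | 0.40 × 0.30 = 12% v 6% | 40% v 6% | 40% v 20% |

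In the first row the PAD-SC comparison satisfies both limits with no effect at all. In the second row the whole-arm rate falls short of 15% although the rate among smokers has doubled. Self-selection into PAD-SC by smokers who want to quit would be expected to widen the PAD-SC contrast further.

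**The case against.** The strongest reply is that (b) is loosely worded rather than wrongly planned. Smoking measures are taken in smokers only, and smoking status is a stratum, so an analyst would probably use smokers anyway. That is a fair guess at the intent. But Table 2 says who is measured, not who is counted, and the only sentence that narrows the comparison narrows it to PAD-SC.

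Second, no section makes 15% and 10% a formal success rule. Statistical Methods compares groups by tests and confidence intervals. With 1:1 allocation stratified by smoking status, non-smokers dilute both arms about equally, so direction and relative size survive. This stands for the whole-arm reading: the absolute difference shrinks by the factor s, but the ratio does not. It does not rescue PAD-SC against the control arm, where the dilution is one-sided.

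Third, a reader might infer that the 15% target is almost out of reach and the 10% limit met almost automatically. The documents do not support that. It needs a smoker share and response rates that they do not give, and the event also counts an undefined reduction ("will give up smoking or have significantly reduced their daily smoking"), so rates of 30% to 50% among smokers cannot be excluded. At s = 50%, a 40% rate reaches the target with probability 0.86, and a 20% control rate stays within its limit with probability only 0.47.

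Last, the whole-person threshold is sensitive to rounding: 10/67 = 14.93% would print as 15%. At s = 30% that lowers the rate needed from 55% to 50%, and with a true 30% rate it raises the chance of success from 1.7% to 4.8%. The pattern is unchanged.

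**Conclusion.** The point holds as a defect in the definition of the denominator. For any smoker share below 100%, the wording of (b) multiplies both limits, as applied to smokers, by 1/s. That needs only two facts: non-smokers are enrolled, and they cannot respond. The competing PAD-SC definition is a second distortion, of a different kind, and the two cannot both be followed.

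The size depends on s. Only at about 15% smokers or fewer is the whole-arm target out of reach by arithmetic alone (0.15/0.15 = 100% of smokers). Above that, difficulty varies widely: the same 40% rate among smokers reaches the target with probability 0.13 at s = 30% and 0.86 at s = 50%. A claim that the plan will return a wrong verdict on the app would also go too far, since the limits are hypotheses and not a decision rule. What can be said is that the percentages reported under (b) could not be read as cessation-or-reduction rates, and that meeting the limits would reflect recruitment mix as well as the app. This is a secondary hypothesis, but the wording should be corrected before the smoking data are analysed.

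**What to change.** Use one denominator throughout: in each arm, all randomised participants recorded as smokers at baseline, whatever pathway they later choose. It has to be written in three places:

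- Hypothesis (b): attach both the 15% and the 10% to baseline smokers randomised to that arm.
- The secondary-outcome sentence at the opening of Section III: replace the PAD-SC versus control comparison. If only (b) is edited, the contradiction remains.
- Statistical Methods: compare the two proportions within the smoker stratum and report the difference with a 95% CI.

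Stating the expected number of smokers per arm and defining what counts as a significant reduction would complete the definition; the new denominator does not settle either.

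The cost is a few sentences and no new data, since baseline smoking status is already a randomisation stratum and the comparison stays randomised. The downside is that the stated sample for (b) becomes smokers only, so its precision looks less favourable. Little real power is lost on the stated rates: 15% v 10% has about 14% power with 67 per arm even if everyone smoked (686 per arm would be needed for 80%), and about 7% with 20 smokers per arm. The result for (b) is therefore better presented as an estimate with its interval.

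### Hypotheses (b) and (c) are worded as separate cut-offs for each arm, are not linked to the planned tests, and leave the comparison set for smoking inconsistent

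*Combined protocol and SAP*

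**What the plan says.** Section II (Specific Aim, Hypotheses) sets out (b) and (c) as one percentage per arm at the end of 12 weeks.

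- **(b)** At least 15% of intervention-arm "participants will give up smoking or have significantly reduced their daily smoking compared to less than" a control limit; the control clause in full is "compared to less than $\leq 10\%$ in the control arm". The control limit is written both as a strict and as a non-strict inequality.
- **(c)** At least 50% "of interventional treatment arm participants will improve their medication adherence from pre- until post-intervention as compared to" under 30% of controls.

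Neither hypothesis states a difference, a ratio or a rule for judging it.

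Section IV, Statistical Methods, says that changes in each outcome "will be compared between and within the groups using t-tests or non-parametric statistical tests as appropriate". It adds: "For the between-group differences, 95% Confidence Intervals will be reported". Significance is two-sided at 5%. No test for proportions is named, and nothing refers back to (b) or (c).

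Section IV, Secondary Outcomes, lists change in daily smoking and improvement in medication adherence. It gives no definition of a responder for either.

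The set of patients for smoking differs between places. Hypothesis (b) speaks of intervention-arm participants. The secondary outcome in Section III compares the PAD-SC group with the control arm. PAD-SC consists of intervention-arm smokers who want help to quit, and that help is offered after the first week of the programme. Randomisation is stratified by site and smoking status (Section III, Study procedures).

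**The concern.** A limit on each arm's observed rate does not measure the treatment effect. An upper limit on the control rate turns a good control result into a failure, however large the gap between arms. Control improvement is plausible here, because controls receive cessation advice, optimised secondary prevention and encouragement to adhere. In the other direction, small numbers of smokers could meet both limits in (b) by chance. A report could then say that a hypothesis was met while the test shows nothing, or that it failed while the test shows a clear benefit.

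The set matters as well. If (b) counts all intervention-arm participants, non-smokers dilute the rate. If it counts PAD-SC only, smokers who chose help after randomisation are compared with an unselected control arm, and randomisation does not protect that comparison.

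**Working it through.** **Inputs.** The limits 15%/10% and 50%/30% are from Section II. The 67 per arm (134 in total) is from Section III, Subject enrollment. The number of smokers is not in the documents; 20 to 33 per arm (30% to 50% of 67) is assumed.

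**The plan's own figure.** The only sample-size calculation is for walking. For a repeated-measures ANOVA, group-by-time interaction, two time points: λ = f²·N·m/(1−r) = 0.0225 × 134 × 2 / 0.75 = 8.04 on 1 and 132 df, giving power 0.804. The 134 is reproduced. Neither (b) nor (c) has a calculation.

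**Method.** For n per arm, the chance of meeting the wording is P(X_I ≥ lower limit) × P(X_C ≤ upper limit), with independent binomial counts.

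**Hypothesis (c), 67 per arm.** At least 50% means at least 34 patients; under 30% means at most 20.

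- True 65% v 40%: P(X_I ≥ 34) = 0.994 and P(X_C ≤ 20) = 0.056, so the product is 0.056. Exact Fisher power for the same rates is 0.778.
- Example: 44/67 v 27/67 is 65.7% v 40.3%, a difference of 17/67 = 25 points (Newcombe 95% CI 8 to 40), Fisher P=0.005. It fails because 40.3% is not under 30%.
- True 40% in both arms: 0.003, so (c) is hardly ever met by chance at that rate.

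**Hypothesis (b), assumed 20 smokers per arm.** At least 15% means at least 3.

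| Result | Control limit read as ≤10% | Read as <10% | Fisher P |
|---|---|---|---|
| 3/20 v 2/20 | met | not met | 1.00 |
| 3/20 v 1/20 | met | met | 0.60 |
| 8/20 v 4/20 | not met | not met | 0.30 |

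Probability that (b) is met:

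| n per arm | True 12% v 12%, ≤10% | Same, <10% | True 40% v 20%, ≤10% | Same, <10% |
|---|---|---|---|---|
| 20 | 0.246 | 0.126 | 0.205 | 0.069 |
| 25 | 0.144 | 0.144 | 0.098 | 0.098 |
| 30 | 0.146 | 0.082 | 0.123 | 0.044 |
| 33 | 0.156 | 0.156 | 0.081 | 0.081 |
| 67 (all participants) | 0.051 | 0.051 | 0.012 | 0.012 |

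In every row the wording is met more often with no effect at 12% than with a doubling from 20% to 40%.

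**Denominator.** At 67 per arm, (b) needs at least 11 responders against at most 6. If 30% smoke (20 of 67), 11 responders are 11/20 = 55% of the arm's smokers. The same 15% is therefore a very different target depending on the set.

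**The case against.** The strongest reply is that these are hypotheses, meaning what the authors expect, and not decision rules. That is right as far as it goes. No section says that observed rates will be checked against the limits or that a hypothesis will be declared met or failed. Both sentences are also comparative in form.

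A reader might infer that no planned test compares the arms on these outcomes. The documents do not support that. Statistical Methods covers each outcome, smoking and adherence are listed outcomes, and non-parametric tests used as appropriate could include a test for binary data. A 3/20 v 2/20 result would be reported with a wide interval. What stands is narrower: no test for proportions is named, no responder is defined, and nothing links the tests to (b) or (c).

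A reader might also infer that 3/20 v 2/20 plainly confirms (b). That needs the ≤10% reading and a denominator of smokers. With all 67 per arm the smallest gap that meets (b) is five patients (11 v 6), and the chance of meeting it at 12% in both arms is about 5%.

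Two further points are fair. A true 40% v 20% is hard to detect by any method with 20 smokers per arm: Fisher power is 0.19, close to the 0.205 chance of meeting the limits. For (c), a true control rate of 40% contradicts the stated expectation, so failing the literal statement is logically correct. That is still the difficulty: the statement tests the guess about controls together with the effect of the app.

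**Conclusion.** The concern holds as a matter of wording and linkage, not as proof of a faulty formal decision rule. Section II gives per-arm limits, and no other formulation of success is offered for smoking or adherence.

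The (c) result is the firmer one. It uses the planned 67 per arm and an illustrative true 65% v 40%, where the literal wording is met in about 6% of trials against 78% Fisher power. The (b) figures rest on an assumed 20 to 33 smokers per arm and, where 10% of n is a whole number, on how the control limit is read. They show that a difference of one or two patients can meet the wording if smokers are that few.

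The inconsistent set for (b) needs no assumption. One version includes non-smokers, and the other is not a randomised comparison.

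Both are secondary hypotheses. The primary walking outcome and its sample size are unaffected.

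**What to change.** In Section II, restate (b) and (c) as between-arm differences in proportions at week 12. In Section IV:

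- **Set.** For (b), all randomised baseline smokers in both arms, not PAD-SC only; stratification by smoking status makes this set ready to use. For (c), all randomised patients. State how a missing week-12 value is counted.
- **Responder.** Define what counts as significantly reduced smoking and as improved adherence. Without this no proportion can be computed.
- **Analysis.** Report the risk difference with a 95% CI, name the test and the interval method, and apply the two-sided 5% rule already in the plan. Stratifying by site is optional, since strata of smokers may be sparse.
- **Wording.** Resolve the double inequality in the control limit of (b), and label 15%/10% and 50%/30% as planning expectations.

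The cost is text only: no new data and no change in sample size. The downside is that the smoking result will usually be imprecise. Power for 15% v 10% is about 7% to 10% with 20 to 40 smokers per arm, and 80% would need 686 per arm. For 50% v 30%, power is about 66% at 67 per arm, and 80% would need 93. It is better to state that imprecision in advance than to leave it hidden behind per-arm limits.
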